10 ADVERSE EVENTS: LIST AND REPORTING REQUIREMENTS

Adverse event (AE) monitoring and reporting is a routine part of every clinical trial. The following list of AEs (Section 10.1) and the characteristics of an observed AE (Sections 10.2 and 10.3) will determine whether the event requires expedited reporting via the CTEP Adverse Event Reporting System (CTEP-AERS) **in addition** to routine reporting.

10.1 Comprehensive Adverse Events and Potential Risks Lists (CAEPR) for Birinapant (TL32711, NSC 756502)

The Comprehensive Adverse Events and Potential Risks list (CAEPR) provides a single list of reported and/or potential adverse events (AE) associated with an agent using a uniform

presentation of events by body system. In addition to the comprehensive list, a subset, the Specific Protocol Exceptions to Expedited Reporting (SPEER), appears in a separate column and is identified with bold and italicized text. This subset of AEs (SPEER) is a list of events that are protocol specific exceptions to expedited reporting to NCI (except as noted below). Refer to the 'CTEP, NCI Guidelines: Adverse Event Reporting Requirements' http://ctep.cancer.gov/protocolDevelopment/electronic_applications/docs/aeguidelines.pdf for further clarification. The CAEPR does not provide frequency data; refer to the Investigator's Brochure for this information. Below is the CAEPR for Birinapant.

NOTE: Report AEs on the SPEER **ONLY IF** they exceed the grade noted in parentheses next to the AE in the SPEER. If this CAEPR is part of a combination protocol using multiple investigational agents and has an AE listed on different SPEERs, use the lower of the grades to determine if expedited reporting is required.

Version 1.2, June 26, 2018([23](#))

Adverse Events with Possible Relationship to Birinapant (CTCAE 5.0 Term)	Specific Protocol Exceptions to Expedited Reporting (SPEER)
BLOOD AND LYMPHATIC SYSTEM DISORDERS	
Anemia	
Febrile neutropenia	
GASTROINTESTINAL DISORDERS	
Diarrhea	
Nausea	
Vomiting	Vomiting (Gr 2)
GENERAL DISORDERS AND ADMINISTRATION SITE CONDITIONS	
Fatigue	Fatigue (Gr 2)
Fever	
IMMUNE SYSTEM DISORDERS	
Cytokine release syndrome	
INVESTIGATIONS	
Lymphocyte count decreased	Lymphocyte count decreased (Gr 2)
METABOLISM AND NUTRITION DISORDERS	
Anorexia	
NERVOUS SYSTEM DISORDERS	
Facial nerve disorder(24)	
Headache	
SKIN AND SUBCUTANEOUS TISSUE DISORDERS	

Adverse Events with Possible Relationship to Birinapant (CTCAE 5.0 Term)	Specific Protocol Exceptions to Expedited Reporting (SPEER)
Rash maculo-papular	
VASCULAR DISORDERS	
Hypotension	

¹This table will be updated as the toxicity profile of the agent is revised. Updates will be distributed to all Principal Investigators at the time of revision. The current version can be obtained by contacting [contact]. Your name, the name of the investigator, the protocol and the agent should be included in the e-mail.

²Facial nerve disorder may manifest itself as Bell's palsy possibly secondary to cytokine release syndrome.

Adverse events reported on birinapant trials, but for which there is insufficient evidence to suggest that there was a reasonable possibility that birinapant caused the adverse event:

BLOOD AND LYMPHATIC SYSTEM DISORDERS - Blood and lymphatic system disorders - Other (pancytopenia)

CARDIAC DISORDERS - Restrictive cardiomyopathy

EYE DISORDERS - Eye disorders - Other (diplopia)

GASTROINTESTINAL DISORDERS - Abdominal pain; Constipation; Dyspepsia; Typhlitis

INFECTIONS AND INFESTATIONS - Infections and infestations - Other (V. zoster infection); Lung infection; Sepsis; Skin infection

INVESTIGATIONS - Alanine aminotransferase increased; Aspartate aminotransferase increased; Lipase increased; Platelet count decreased; Serum amylase increased

METABOLISM AND NUTRITION DISORDERS - Dehydration; Hypophosphatemia

MUSCULOSKELETAL AND CONNECTIVE TISSUE DISORDERS - Myalgia

RENAL AND URINARY DISORDERS - Acute kidney injury

Note: Birinapant in combination with other agents could cause an exacerbation of any adverse event currently known to be caused by the other agent, or the combination may result in events never previously associated with either agent.

10.2 Adverse Event Characteristics

- **CTCAE term (AE description) and grade:** The descriptions and grading scales found in the revised NCI Common Terminology Criteria for Adverse Events (CTCAE) version 5.0 will be utilized for AE reporting. All appropriate treatment areas should have access to a copy of the CTCAE version 5.0. A copy of the CTCAE version 5.0 can be downloaded from the CTEP web site http://ctep.cancer.gov/protocolDevelopment/electronic_applications/ctc.htm.
- **For expedited reporting purposes only:**
 - AEs for the agent that are ***bold and italicized*** in the CAEPR (*i.e.*, those listed in the SPEER column, Section (10.1 CAEPR for Birinapant) should be reported through CTEP-AERS only if the grade is above the grade provided in the SPEER.
 - Other AEs for the protocol that do not require expedited reporting are outlined in section 10.3.3.

- **Attribution** of the AE:
 - Definite – The AE is *clearly related* to the study treatment.
 - Probable – The AE is *likely related* to the study treatment.
 - Possible – The AE *may be related* to the study treatment.
 - Unlikely – The AE is *doubtfully related* to the study treatment.
 - Unrelated – The AE is *clearly NOT related* to the study treatment.

10.3 Expedited Adverse Event Reporting

10.3.1 Rave-CTEP-AERS Integration

The Rave Cancer Therapy Evaluation Program Adverse Event Reporting System (CTEP-AERS) integration enables evaluation of post-baseline AEs entered in Rave to determine whether they require expedited reporting and facilitates entry in CTEP-AERS for those AEs requiring expedited reporting.

All AEs that occur after baseline are collected in Medidata Rave using the Adverse Event form, which is available for entry at each treatment or reporting period and is used to collect AEs that start during the period or persist from the previous reporting period. CRA will enter AEs that occur prior to the start of treatment on a baseline form that is not included in the Rave-CTEP-AERS integration. AEs that occur prior to enrollment must begin and end on the baseline Adverse Event form and should not be included on the standard Adverse Events form that is available at treatment unless there has been an increase in grade.

Prior to sending AEs through the rules evaluation process, site staff should verify the following on the Adverse Event form in Rave:

- The reporting period (course/cycle) is correct, and
- AEs are recorded and complete (no missing fields) and the form is query-free.

The CRA reports AEs in Rave at the time the Investigator learns of the event. If the CRA modifies an AE, it must be re-submitted for rules evaluation.

Upon completion of AE entry in Medidata Rave, the CRA submits the AE for rules evaluation by completing the Expedited Reporting Evaluation form. Both NCI and protocol-specific reporting rules evaluate the AEs submitted for expedited reporting. A report is initiated in CTEP-AERS using information entered in Medidata Rave for AEs that meet reporting requirements. The CRA completes the report by accessing CTEP-AERS via a direct link on the Medidata Rave Expedited Reporting Evaluation form.

In the rare occurrence that Internet connectivity is lost, a 24-hour notification is to be made to CTEP by telephone at [contact]. Once internet connectivity is restored, the 24-hour notification that was phoned in must be entered immediately into CTEP-AERS using the direct link from Medidata Rave.

Additional information about the CTEP-AERS integration is available on the CTSU website:

- Study specific documents: Protocols > Documents > Education and Promotion, and
- Expedited Safety Reporting Rules Evaluation user guide: Resources > CTSU Operations Information > User Guides & Help Topics.

NCI requirements for SAE reporting are available on the CTEP website:

- NCI Guidelines for Investigators: Adverse Event Reporting Requirements is available at
https://ctep.cancer.gov/protocolDevelopment/electronic_applications/docs/aeguidelines.pdf.

10.3.2 Distribution of Adverse Event Reports

CTEP-AERS is programmed for automatic electronic distribution of reports to the following individuals: Principal Investigator and Adverse Event Coordinator(s) (if applicable) of the Corresponding Organization or Lead Organization, the local treating physician, and the Reporter and Submitter. CTEP-AERS provides a copy feature for other e-mail recipients.

10.3.3 Expedited Reporting Guidelines

Use the NCI protocol number and the protocol-specific patient ID assigned during trial registration on all reports.

Note: : A death on study requires both routine and expedited reporting, regardless of causality as long as the death occurred within 30 days after the last administration of the investigational agent. A death on study more than 30 days after last treatment requires both routine and expedited reporting, only if attribution to study intervention is possible, probably or definite. Attribution to treatment or other cause must be provided.

Death due to progressive disease should be reported as **Grade 5 “Neoplasms benign, malignant and unspecified (incl cysts and polyps) - Other (Progressive Disease)”** under the system organ class (SOC) of the same name. Evidence that the death was a manifestation of underlying disease (e.g., radiological changes suggesting tumor growth or progression: clinical deterioration associated with a disease process) should be submitted.

Phase 1 and Early Phase 2 Studies: Expedited Reporting Requirements for Adverse Events that Occur on Studies under an IND/IDE within 30 Days of the Last Administration of the Investigational Agent/Intervention ^{1, 2}

FDA REPORTING REQUIREMENTS FOR SERIOUS ADVERSE EVENTS (21 CFR Part 312)

NOTE: Investigators MUST immediately report to the sponsor (NCI) ANY Serious Adverse Events, whether or not they are considered related to the investigational agent(s)/intervention (21 CFR 312.64)

An adverse event is considered serious if it results in ANY of the following outcomes:

- 1) Death
- 2) A life-threatening adverse event
- 3) An adverse event that results in inpatient hospitalization or prolongation of existing hospitalization for \geq 24 hours
- 4) A persistent or significant incapacity or substantial disruption of the ability to conduct normal life functions
- 5) A congenital anomaly/birth defect.
- 6) Important Medical Events (IME) that may not result in death, be life threatening, or require hospitalization may be

considered serious when, based upon medical judgment, they may jeopardize the patient or subject and may require medical or surgical intervention to prevent one of the outcomes listed in this definition. (FDA, 21 CFR 312.32; ICH E2A and ICH E6).

ALL SERIOUS adverse events that meet the above criteria MUST be immediately reported to the NCI via electronic submission within the timeframes detailed in the table below.

Hospitalization	Grade 1 and Grade 2 Timeframes	Grade 3-5 Timeframes
Resulting in Hospitalization ≥ 24 hrs	10 Calendar Days	24-Hour 5 Calendar Days
Not resulting in Hospitalization ≥ 24 hrs	Not required	

NOTE: Protocol specific exceptions to expedited reporting of serious adverse events are found in the Specific Protocol Exceptions to Expedited Reporting (SPEER) portion of the CAEPR.

Expedited AE reporting timelines are defined as:

- “24-Hour; 5 Calendar Days” - The AE must initially be submitted electronically within 24 hours of learning of the AE, followed by a complete expedited report within 5 calendar days of the initial 24-hour report.
- “10 Calendar Days” - A complete expedited report on the AE must be submitted electronically within 10 calendar days of learning of the AE.

¹Serious adverse events, with the exception of expected long-term radiation effects, that occur more than 30 days after the last administration of investigational agent/intervention and have an attribution of possible, probable, or definite require reporting as follows:

Expedited 24-hour notification followed by complete report within 5 calendar days for:

- All Grade 3, 4, and Grade 5 AEs

Expedited 10 calendar day reports for:

- Grade 2 AEs resulting in hospitalization or prolongation of hospitalization

²For studies using PET or SPECT IND agents, the AE reporting period is limited to 10 radioactive half-lives, rounded UP to the nearest whole day, after the agent/intervention was last administered. Footnote “1” above applies after this reporting period.

Effective Date: May 5, 2011

10.3.4 Additional Protocol-Specific Expedited Adverse Event Reporting Exclusions

No exclusions.

10.4 Routine Adverse Event Reporting

All Adverse Events **must** be reported in routine study data submissions. **AEs reported expeditiously through CTEP-AERS must also be reported in routine study data submissions.**

Adverse event data collection and reporting, which are required as part of every clinical trial, are done to ensure the safety of patients enrolled in the studies as well as those who will enroll in

future studies using similar agents. AEs are reported in a routine manner at scheduled times during the trial using Medidata Rave. For this trial the Adverse Event CRF is used for routine AE reporting in Rave.

10.5 Pregnancy

Although not an adverse event in and of itself, pregnancy as well as its outcome must be documented via **CTEP-AERS**. In addition, the **Pregnancy Information Form** included within the NCI Guidelines for Adverse Event Reporting Requirements must be completed and submitted to CTEP. Any pregnancy occurring in a patient or patient's partner from the time of consent to 90 days after the last dose of study drug must be reported and then followed for outcome. Newborn infants should be followed until 30 days old. Please see the "NCI Guidelines for Investigators: Adverse Event Reporting Requirements for DCTD (CTEP and CIP) and DCP INDs and IDEs" (at http://ctep.cancer.gov/protocolDevelopment/adverse_effects.htm) for more details on how to report pregnancy and its outcome to CTEP.

10.6 Secondary Malignancy

A *secondary malignancy* is a cancer caused by treatment for a previous malignancy (e.g., treatment with investigational agent/intervention, radiation or chemotherapy). A secondary malignancy is not considered a metastasis of the initial neoplasm.

CTEP requires all secondary malignancies that occur following treatment with an agent under an NCI IND/IDE be reported expeditiously via CTEP-AERS. Three options are available to describe the event:

- Leukemia secondary to oncology chemotherapy (e.g., acute myelocytic leukemia [AML])
- Myelodysplastic syndrome (MDS)
- Treatment-related secondary malignancy

Any malignancy possibly related to cancer treatment (including AML/MDS) should also be reported via the routine reporting mechanisms outlined in each protocol.

10.7 Second Malignancy

A second malignancy is one unrelated to the treatment of a prior malignancy (and is **NOT** a metastasis from the initial malignancy). Second malignancies require **ONLY** routine AE reporting unless otherwise specified.

11 STUDY CALENDAR

A time window of -2 days on treatment days and +/- 2 days on non-treatment days will be permitted for weekly physical exam, performance status, routine vital signs, weight and routine labs. Cycle days will be numbered relative to treatment.

Procedure/ Assessment	Screening	Baseline	C1D1 Wk1	C1D2 Wk1	C1D4 Wk1	C1D8 Wk2	C1D9 Wk2	C1D15 Wk3	C2D1 Wk4	C2D2 Wk4	C2D8 Wk5	C2D9 Wk5	C2D15 Wk6	14 Day Safety Visit j, 1	28 Day Post tx Safety Visit j, 1	Long term Follow Up k,1
Informed consent	X	X														
Birinapant ^a						X ^c										
Re-IMRT ^b			X	X	X	X	X	X	X	X	X	X	X	X	X	
Demographics	X															
Medical history	X															
Concurrent meds	X		X				X	X				X		X	X	X ^p
Physical exam ^q	X		X				X	X				X		X	X	
Vital signs	X		X	X ^d		X	X ^d	X	X	X ^d	X	X	X	X	X	
Height		X														
Weight		X	X								X			X	X	
Performance status	X		X								X			X	X	
CBC/diff, platelets	X		X				X	X			X		X	X	X	
Serum chemistry ^e	X		X			X	X	X			X		X	X	X	
PT/PTT/INR	X															
HIV test	X															
ECG ⁿ	X					X					X					
Adverse events		X					X	X			X		X	X	X	
Tumor biopsy f,r		X				X										

Procedure/ Assessment	Screening ≤ 4 weeks of first treatment	Baseline	C1D1 Wk1	C1D2 Wk1	C1D4 Wk1	C1D8 Wk2	C1D9 Wk2	C1D15 Wk3	C2D1 Wk4	C2D2 Wk4	C2D8 Wk5	C2D9 Wk5	C2D15 Wk6	14 Day Post tx Safety Visit j, 1	28 Day Post tx Safety Visit j, 1	Long term Follow Up k, 1
Blood (for control DNA) ^r		X														
Urine HCG ^g	X		X													
Tumor measurements ^h	X															X
Blood for Pharmacokinetics																
Blood for Pharmacogenomics																
Phone call or e-mail																X
Dental Evaluation		X														

- a: Birinapant on days 2 and 9 of every cycle. If a patient misses a dose on each of those days, the infusion can be given up to 2 days later, but the C1D4 biopsy will not be performed.
- b: Standard re-IMRT 2GY/day/5 days a week/ M-F for 6 weeks to 60-66Gy.
- c: Patients will be observed for 30-60 minutes post the first and second infusion of birinapant for adverse events.
- d: Vital signs will be collected prior to and after every birinapant infusion.
- e: Albumin, alkaline phosphatase, total bilirubin, bicarbonate, BUN, calcium, chloride, creatinine, glucose, LDH, phosphorus, potassium, total protein, SGOT [AST], SGPT [ALT], sodium, magnesium, uric acid, amylase, lipase.
- f: All attempts will be made to obtain optional tumor biopsies within 28 days before treatment and on C1D4 for biomarkers studies. A blood sample for control DNA will be drawn and sent together with the pre-treatment tumor biopsy.
- g: Women of childbearing potential only.
- h: Tumor measurements within 6 weeks pre-treatment (PET/CT and CT or MRI neck/upper abdomen with contrast), at 3 (+/- 2 weeks, PET/CT and CT or MRI with contrast), 6 (+/- 4 weeks, CT or MRI with contrast), 9 (+/- 4 weeks, CT or MRI with contrast), 12 (+/- 4 weeks, CT or MRI with contrast), 18 (+/- 4 weeks, CT or MRI with contrast), 24 (+/- 4 weeks, CT or MRI with contrast) months post-radiation treatment. Evaluations will be stopped after confirmation of disease progression. MRI neck with gadolinium and PET/CT can substitute CT with contrast if patient has contrast allergy.
- i: Pharmacokinetics samples will be drawn within 60 minutes prior to start of infusion and within 60 minutes after end of infusion of the birinapant. Dates and exact times of start and stop of the infusions and sample collection dates and times will be noted in the PK sheet
- j: Patients will be invited for safety follow up visits approximately 14 (+/- 3) days and 28 (+/- 7) days after completion of treatment. Patients removed from treatment for unacceptable adverse event(s) will be followed until resolution or stabilization of the adverse event.

k: Patients will be clinically evaluated at 3 (+/- 2 weeks), 6 (+/- 4 weeks), 9 (+/- 4 weeks), 12 (+/- 4 weeks), 18 (+/- 4 weeks), 24 (+/- 4 weeks) months after completion of treatment. These visits will be stopped after confirmation of disease progression. After completion of visits, participants will be followed by phone or email every 6 months for survival for up to 2 years.

l: If patients are unable or unwilling to come to these visits, they will be contacted by phone or e-mail for survival. After progression, participants will be followed every six months for survival.

m: On C1D4 a PK sample will be collected within +/- 4h of the biopsy. Dates and exact times of start and stop of the infusions and sample collection dates and times will be noted in the PK sheet.

n: An ECG will be performed within 2 hours of the start of infusion and within 2 hours after infusion completion and QTcF will be evaluated by the PI or clinician AI.

o: New AEs will be captured through the first 3-month follow-up visit, with the exception of SAEs considered possibly, probably or definitely related to study agents, which will continue to be reported per section **10.3.3**.

p: Concurrent medications will be captured up through the first 3-month follow up visit.

q: Physical exam and clinic evaluation should occur 1-5 working days prior to bimonthly infusion.

r: Research specimens should be collected only after subject has signed consent and all eligibility criteria have been met.

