1 OBJECTIVES

1.1 Primary Objectives

- Determine the toxicities and maximum tolerated dose (MTD) of birinapant concurrent with intensity modulated re-irradiation therapy (IMRRT).

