6.2 Definition of Dose-Limiting Toxicity

Dose-limiting toxicity (DLT) will be defined as any one of the following adverse events, possibly attributable to the combination of birinapant and radiotherapy, that occur within 42 days of the start of therapy:

- Any grade 5 toxicities.

- Any grade ≥ 4 hematologic toxicity except for lymphopenia.
- Any grade ≥ 3 non-hematologic toxicity, **except for any of the following:**
 - nausea and vomiting that can be managed with standard supportive care over 2 weeks
 - alopecia,
 - drug-related fever,
 - radiation-induced in-field related side effects, including but not limited to dermatitis, oral mucositis and related pain, dysphagia, dysgeusia, esophagitis, xerostomia, weight loss, thickened oral secretions that can be managed with standard supportive care over 2 weeks
 - isolated laboratory abnormalities without clinical sequelae
- \geq grade 3 prolonged (> 7 days) serum amylase or lipase elevation*
- \geq grade 3 prolonged (> 7 days) aspartate aminotransferase (AST) elevation*
- \geq grade 3 prolonged (> 7 days) alanine aminotransferase (ALT) elevation*
- Concurrent elevation of AST/ALT > 3 times the upper limit of normal and bilirubin > 2 times the upper limit of normal (i.e., Hy's law)
- Any grade toxicity that mandates discontinuation of birinapant treatment for more than 2 weeks

* all of which will be considered to be dose limiting.

Grade 5 AEs are unacceptable, though the chances of their occurrence are considered to be quite low. The probability of DLTs with birinapant in combination with radiotherapy at the specified dose levels are expected not to exceed 30% of patients. All AEs \leq grade 4 are considered acceptable in terms of risk, given that the median overall survival of patients with locoregionally recurrent head and neck cancer who have received 1 or 2 lines of standard of care treatment is very short (approximately 3-6 months).

Criteria are based on the NCI Common Terminology Criteria for Adverse Events, Version 5.0.

Dose escalation will proceed within each dose level according to the following scheme. Dose-limiting toxicity (DLT) is defined above.

Number of Patients with DLT at a Given Dose Level	Escalation Decision Rule
0 out of 3	Enter 3 patients at the next dose level.

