6.3 Dose Expansion Cohort

Birinapant will be administered IV over 30 minutes on days 2 and 9 of every cycle at the MTD estimated during dose escalation part of the study.

IMRRT will be administered starting on Day 1 at 2Gy/day x 5 days/week/M-F for 2 cycles (6 weeks) to a total of 60-66Gy.

IMRRT will start within 1-4h after the infusion of birinapant.

The study team will meet weekly to review the ongoing results of the trial and will continue to monitor and record AEs during the dose expansion portion of the study.

An expansion cohort of 10 additional patients will be treated at the MTD and the results combined with those of patients at the MTD to obtain improved estimates of safety and toxicity as well as to perform analyses to address secondary objectives.

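### After the 3-month visit, non-serious adverse events and expected late radiation effects are not systematically collected, although toxicity is a primary endpoint and clinic follow-up runs to 24 months

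*Combined protocol and SAP*

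**What the plan says.** - **Collection window.** Section 11, footnote o: "New AEs will be captured through the first 3-month follow-up visit". Beyond that visit the footnote keeps only serious events with at least a possible link to the study agents, and refers these to Section 10.3.3.
- **The route that remains.** Section 10.3.3, footnote 1, requires related serious events to be reported beyond 30 days after the last administration, "with the exception of expected long-term radiation effects".
- **Follow-up.** Section 11, footnote k, schedules clinical evaluation at 3, 6, 9, 12, "18 (+/- 4 weeks), 24 (+/- 4 weeks) months after completion of treatment", and adds: "These visits will be stopped after confirmation of disease progression". Survival contact follows.
- **Aims.** Section 1.1 makes the toxicities of birinapant with re-irradiation, as well as the MTD, the primary objective. Section 9.2 names other toxicities beside DLTs as primary endpoints. Section 6.3 adds ten patients at the MTD partly "to obtain improved estimates of safety and toxicity".
- **General reporting rule.** Section 10.4 requires all adverse events in routine data submissions, and Section 10.3.1 says those after baseline are entered in Rave. Neither sets an end date.
- **Analysis.** Section 9.3 reports DLTs by dose level and tabulates the toxicities noted. No late-toxicity analysis is described.

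**The concern.** Either rule could be reasonable alone. A phase I trial may close routine adverse event collection early, and an expedited system may leave out events that are already anticipated. The difficulty is the combination. Once routine capture ends, related-SAE reporting is the main route left, and it excepts the class of late event most closely tied to re-irradiation. Footnote o also speaks of study agents, so it is unclear whether an event attributed to the radiation counts at all.

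Section 2.4 says the toxicities of birinapant with radiation are unknown and raises the possibility that the combination could worsen cranial neuropathy or mucosal toxicity. If an expected radiation effect became more frequent or more severe, the extra events would fall in the excepted class. DLT data cannot fill the gap: the DLT definition covers events "that occur within 42 days of the start of therapy", and Section 6.2 leaves manageable in-field radiation effects out of it. At stake is whether the trial can describe late toxicity in the patients it is already seeing.

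**Working it through.** The plan states no figure on this point, so there is none to reproduce. The check compares the rules and then gauges scale.

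**1. What must be recorded after month 3**

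| Late event | Required? | Source |
|---|---|---|
| Non-serious new event | No | Section 11, footnote o |
| Serious, related, not an expected radiation effect | Yes | Section 10.3.3, footnote 1 |
| Serious, possibly related, classed as an expected radiation effect | No | Section 10.3.3, footnote 1 |
| Death attributed to study intervention | Yes | Section 10.3.3 |
| Secondary malignancy | Yes | Section 10.6 |
| Event that led to removal from treatment | Followed to resolution or stabilization | Section 6.6 |

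Section 10.4, read alone, would turn each No into Yes. Footnote o is the specific rule on the window and probably governs, but the text does not say so.

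**2. Visits and calendar time**

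- Sections 6.6 and 11 list six visits: 3, 6, 9, 12, 18 and 24 months. Routine capture reaches one; five fall outside it. Sections 12 and 12.1 omit month 18; on that list it is four of five.
- Time outside: 24 − 3 = 21 months, and 21/24 = 87.5% (85% to 90% across the visit windows). This is calendar time, not patient time.

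**3. Chance that at least one late event occurs**

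The documents give no late-event rate, so p is an assumption. The formula is 1 − (1 − p)^n. With n = 16, the MTD group in Section 9.2, all under observation:

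- p = 5%: 1 − 0.95^16 = 56%
- p = 10%: 1 − 0.90^16 = 81%
- p = 20%: 1 − 0.80^16 = 97%
- p = 30%: 1 − 0.70^16 = 99.7%

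The expected number is 16p, that is 0.8 to 4.8 events.

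**4. Attrition**

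Section 2.4 cites local control of nearly 50% at 1 year and 2-year survival of 15% to 38% for re-irradiation with chemotherapy. As rough guides to the number at risk, with p = 10%:

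- 16 × 0.5 = 8 patients: 1 − 0.90^8 = 57%
- 16 × 0.15 = 2.4 and 16 × 0.38 = 6.1, so about 2 to 6 patients: 1 − 0.90^2 = 19% to 1 − 0.90^6 = 47%

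**5. What collection would add**

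If late events were sought and none seen, the two-sided 95% upper limit is 1 − 0.025^(1/n): 20.6% for n = 16 and 36.9% for n = 8. Without systematic collection, no such statement can be made about the uncollected classes.

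**6. Dose finding**

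The DLT window is 42 days from the start of therapy (Section 6.2), or 42 days plus 14 (± 3) days (Section 9.2). Both close before the visit 3 months after treatment, so late events cannot enter the escalation decision.

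**The case against.** Much of the case on the other side stands.

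- **Late toxicity is not wholly lost.** A reader might infer that the trial would report no late toxicity by construction. The table above shows otherwise, and Section 10.4 sends expedited events into the routine data as well, so those events can reach the toxicity tables.
- **Misclassification is possible, not certain.** A reader might infer that any late event worsened by birinapant would be labelled an expected radiation effect. Section 10.1 warns that birinapant may exacerbate events known from the other agent, and an unusually severe event need not be called expected. But the protocol does not define expected in this setting, so the classification is left to judgement.
- **The general rule points the other way.** Sections 10.4 and 10.3.1 have no time limit. That makes this partly a conflict to reconcile, but it does not close the gap while footnote o stands.
- **Few patients may remain at risk.** Section 6.2 puts median survival at about 3 to 6 months for recurrent patients after one or two lines of treatment, and visits stop at progression. This lowers the chance of seeing events. It does not remove the gap, because patients still attending are those in whom late effects can be observed.
- **Better collection would not establish cause.** A reader might hope it would show whether birinapant worsens late damage. With one arm, previously irradiated patients and 3 to 6 patients per escalation level, the data can only describe.

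**Conclusion.** The concern holds in a limited form. After month 3, non-serious events and expected late radiation effects, even serious and possibly related ones, are not systematically collected. That leaves the toxicity part of the primary objective, and the expansion cohort's safety estimates, incomplete for late effects. It does not touch MTD selection, and a reader who inferred that dose decisions are compromised would go beyond the documents.

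The visit count follows directly from the schedule. The probabilities are illustrations: they rest on assumed rates of 5% to 30%, on independence between patients, and on the number still observed. They give the chance that an event occurs, not that it goes unrecorded, since some late events remain reportable. The gap merits correction chiefly because closing it is inexpensive and late findings not written down at the visit may be hard to recover.

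**What to change.** Amend footnote o of Section 11 so that new grade 3 or higher adverse events, including late in-field radiation effects, are recorded regardless of attribution at the existing follow-up visits through 24 months, or until visits stop at progression. Reconcile footnote o with Section 10.4 so that one collection window applies. In the primary endpoint analysis under Section 9.3, add a descriptive table of late events by dose level, with the number of patients still under observation at each visit. The expedited rules in Section 10.3.3 can stay as they are.

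No extra patients or visits are needed. The cost is modest additional CRF entry and data cleaning for at most 34 patients. Section 6.6 describes these visits as tumor evaluations and allows phone or e-mail contact instead, so the amendment should make clear that adverse events are to be asked about, and should mark contacts at which in-field effects could not be examined. The resulting late data will be descriptive only.
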